## **7.3 Informed Consent**

The investigator or qualified designee must obtain documented consent according to ICH-GCP and local regulations, as applicable, from each potential subject or each subject's legally authorized representative prior to participating in the research study. Subjects who agree to participate will sign the approved informed consent form and will be provided a copy of the signed document.

The initial ICF, any subsequent revised written ICF and any written information provided to the subject must be approved by IRB prior to use. The ICF will adhere to IRB/IEC requirements,

applicable laws and regulations.

#### **7.4 Compliance with Trial Registration and Results Posting Requirements**

Under the terms of the Food and Drug Administration Modernization Act (FDAMA) and the Food and Drug Administration Amendments Act (FDAAA), the Sponsor-Investigator of the trial is solely responsible for determining whether the trial and its results are subject to the requirements for submission to <http://www.clinicaltrials.gov>. Information posted will allow subjects to identify potentially appropriate trials for their disease conditions and pursue participation by calling a central contact number for further information on appropriate trial locations and trial site contact information.

#### **7.5 Record Retention**

Essential documents are those documents that individually and collectively permit evaluation of the study and quality of the data produced. After completion of the study, all documents and data relating to the study will be kept in an orderly manner by the Investigator in a secure study file. All subject medical records and other source documentation will be kept for the maximum time permitted by the hospital, institution, or medical practice.

For adverse events, we expect a rate of 10% in the IMRT and RP arms. The main HRQOL endpoint of interest is EPIC-26 sexual function. The estimated number of patients we will evaluate is as follows: AS 300; PGA: 280; SBRT: 288; IMRT: 316; RP: 333. This is based on the incidence of low and intermediate prostate cancer in the SCa and NYS SEER registries.

## APPENDIX A.

### **Baseline Survey**

1. Today's date:   /  /20       

2. What is your birth date:   /  /19     
            

3. When were you first diagnosed with prostate cancer:   /  /20       
            

4. In general, you would say your health is:

- Excellent
- Very good
- Good
- Fair
- Poor
- Very poor

5. What is your most recent PSA result?   .    Don't know

6. What date was this PSA test done?   /  /20       Don't know  
            

7. This next question is about your plans for treatment for prostate cancer or treatment you have already received.

*For each of the following types of treatment, please indicate if you have chosen it, started to receive it, are considering it, or are not considering it at this time. Check one box on each row that best reflects your decision at this time for each type of treatment.*

Type of Treatment	I have chosen this plan and have started or completed it	I have chosen this plan but have not yet received it	I am considering this option but have not made a decision yet	I am not considering this option at this time
a. Active Surveillance (My doctor will monitor how I am doing without directly treating the cancer)	 Date started:    /    /            			
Type of Treatment (Cont.)	I have chosen this plan and have started or	I have chosen this plan but	I am considering this option but	I am not considering this option

	completed it	have not yet received it	have not made a decision yet	
b. Prostate surgery (radical prostatectomy), which would remove the whole prostate.	 Date of surgery: ____/____/____ MM DD YY			
c. HIFU / High Intensity Focused Ultrasound (ultrasound waves cross tissue to destroy the part of the prostate that had cancer)	 Date started: ____/____/____ MM DD YY			
d. Cryotherapy (freezing the part of the prostate that had cancer)	 Date started: ____/____/____ MM DD YY			
e. Laser therapy	 Date started: ____/____/____ MM DD YY			
f. Radio Frequency Ablation	 Date started: ____/____/____ MM DD YY			
g. Photodynamic therapy	 Date started: ____/____/____ MM DD YY			
h. External Beam Radiation Therapy or IMRT (radiation treatment requiring more than 2 weeks of treatment)	 Date started: ____/____/____ MM DD YY			
i. Stereotactic Body Radiation Therapy (SBRT) (radiation treatment requiring less than 2 weeks of treatment)	 Date started: ____/____/____ MM DD YY			

j. Brachytherapy (radioactive seeds) This involves having radioactive seeds placed within the prostate	 Date started: ____/____/____ MM D D YY			
k. Proton Beam Therapy	 Date started: ____/____/____ MM D D YY			
l. Any other type of radiation therapy? Describe: _____	 Date started: ____/____/____ MM D D YY			
m. Hormonal treatments to lower testosterone (e.g. Lupron, Zoladex, Firmagon, Eligard, Vantas, etc)	 Date started: ____/____/____ MM D D YY			
n. Surgical removal of testicles (Orchiectomy)	 Date of surgery: ____/____/____ MM D D YY			
o. Chemotherapy (docetaxel, cabazitaxel, other)	 Date started: ____/____/____ MM D D YY			

### Health Before Treatment

**For the next set of questions, please refer to the time just BEFORE you were diagnosed.**

#### **Urinary Issues**

8. During the 4 weeks before your diagnosis, how often have you leaked urine (pee)? (Choose one)

- More than once a day
- About once a day
- More than once a week
- About once a week
- Rarely or never

9. Which of the following best describes your urinary control (ability to hold pee) **during the 4 weeks before your diagnosis?** (Choose one)

- No urinary control whatsoever
- Frequent dribbling
- Occasional dribbling
- Total control

10. How many pads or adult diapers per day did you usually use to control leakage (pee) **during the 4 weeks before your diagnosis?** (Choose one)

- None
- 1 pad per day
- 2 pads per day
- 3 or more pads per day

11. How big a problem, if any, has each of the following been for you **during the 4 weeks before your diagnosis?** (Choose one for each item)

	No problem	Very small problem	Small problem	Moderate problem	Big problem
a. Dripping or leaking urine (pee)					
b. Pain or burning on urination (when peeing)					
c. Bleeding with urination (pee)					
d. Weak urine stream (pee) or incomplete emptying					
e. Need to urinate (pee) frequently during the day					

12. Overall, how big a problem has your urinary function (ability to pee) been for you **during the 4 weeks before your diagnosis?** (Choose one)

- No problem
- Very small problem
- Small problem
- Moderate problem

Big problem

### Bowel Issues

13. How big a problem, if any, has each of the following been for you **during the 4 weeks before your diagnosis?**  
*(Choose one response on each line)*

	No problem	Very small problem	Small problem	Moderate problem	Big problem
a. Urgency to have a bowel movement (poop)					
b. Increased frequency of bowel movements (poop)					
c. Losing control of your stools (poop)					
d. Bloody stools (blood with poop)					
e. Abdominal/pelvic/rectal pain					

14. Overall, how big a problem have your bowel habits (ability to poop) been for you **during the 4 weeks before your diagnosis?** *(Choose one)*

- No problem
- Very small problem
- Small problem
- Moderate problem
- Big problem

### Sexual Issues

15. How would you rate each of the following **during the 4 weeks before your diagnosis?**  
*(Choose one response on each line)*

	Very poor to none	Poor	Fair	Good	Very good
a. Your ability to have an erection (hard on)?					
b. Your ability to reach orgasm (climax)?					

16. How would you describe the usual **QUALITY** of your erections (hard on) **during the 4 weeks before your diagnosis?** *(Choose one)*

- None at all
- Not firm enough for any sexual activity

- Firm enough for masturbation and foreplay only
- Firm enough for intercourse

17. How would you describe the FREQUENCY of your erections (hard on) **during the 4 weeks before your diagnosis?** (Choose one)

- I NEVER had an erection when I wanted one
- I had an erection LESS THAN HALF the time I wanted one
- I had an erection ABOUT HALF the time I wanted one
- I had an erection MORE THAN HALF the time I wanted one
- I had an erection WHENEVER I wanted one

18. Overall, how would you rate your ability to function sexually **during the 4 weeks before your diagnosis?** (Choose one)

- Very poor
- Poor
- Fair
- Good
- Very good

19. Overall, how big a problem has your sexual function, or lack of sexual function, been for you **during the 4 weeks before your diagnosis?** (Choose one)

- No problem
- Very small problem
- Small problem
- Moderate problem
- Big problem

20. How big a problem **during the 4 weeks before your diagnosis** was each of the following for you? (Choose one response on each line)

	No problem	Very small problem	Small problem	Moderate problem	Big problem
a. Feeling depressed					
b. Lack of energy					
c. Change in body weight					

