## 1. Protocol Summary

Full Title:	Prostate Cancer Comparative Outcomes of New Conceptual Paradigms for Treatment
Short Title:	PC CONCEPT
Principal Investigators:	[name] MPH; [name] MPH
Study Description:	This study will use a population-based cohort design to study men with newly diagnosed low- and intermediate-risk prostate cancer at high-volume centers in Southern California (SCa) and New York State (NYS). Complications of contemporary treatments for prostate cancer and quality of life outcomes, such as general health, urinary, sexual, and bowel function, cancer anxiety, and treatment regret will be compared and tracked over the course of this study.
Sample Size:	N= 3,657
Enrollment:	This study will enroll 2,378 subjects and screen up to 3,657 subjects.
Study Population:	Subjects will have pathologically-confirmed clinically localized prostate adenocarcinoma with National Comprehensive Cancer Network (NCCN) low (T1-T2a, Gleason 6, Grade Group 1, PSA <10 ng/mL) or intermediate risk (T2b-T2c or, Gleason 7, Grade Group 2 or 3 or PSA 10-20 ng/mL) at one of the selected hospitals in SCa and NYS. Subjects must also have a diagnosis date during the 18-month recruitment window.
Enrollment Period:	18 months
Study Design:	Prospective, observational
Description of Sites	Patient enrollment at 15 sites within SCa and NYS, identified through National Cancer Institute-sponsored Surveillance Epidemiology and End Results (SEER)
Study Duration:	01Oct2020 - 30Nov2023
Participant Duration:	12 months
Primary Objectives:	To measure the self-reported, overall and disease specific health related quality of life (HRQOL) prior to treatment, at 8 months, and 12 months following active surveillance (AS), SBRT, IMRT, PGA, and RP.

To define and compare the rate of adverse events following stereotactic body radiation therapy (SBRT), partial gland ablation (PGA), intensity modulated radiation therapy (IMRT) and radical prostatectomy (RP) among men recently diagnosed with low and intermediate risk prostate cancer.

Primary Endpoints:	Change from Baseline in Patient-Reported Quality of Life as Measured on EQ-5D-5L at 8 Months & 12 Months following Treatment
	Change from Baseline in Patient-Reported Urinary, Sexual, and Bowel Function as Measured on EPIC-26 at 8 Months & 12 Months following Treatment

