#### **Sexual Issues**

24. Do you currently use any of the following to help with problems with sexual function? (Choose one response on each line)

		Yes	No
a.	Vacuum suction device		
b.	Penile injections (shots)		
c.	Pills, such as Viagra, Cialis, Levitra, Staxyn, Stendra		
d.	Urethral pellets or suppositories (Muse)		
e.	Penile prosthesis (surgical implant)		
f.	Other (please specify): _____		

25. How would you rate each of the following **during the past 4 weeks?**

(Choose one response on each line)

	Very poor to none	Poor	Fair	Good	Very good
a.	Your ability to have an erection (getting hard for sex)?				
b.	Your ability to reach orgasm (climax)?				

26. How would you describe the usual **QUALITY** of your erections (getting hard for sex) **during the past 4 weeks?**  
(Choose one)

- None at all
- Not firm enough for any sexual activity
- Firm enough for masturbation and foreplay only
- Firm enough for intercourse

27. How would you describe the **FREQUENCY** of your erections (getting hard for sex) **during the past 4 weeks?**  
(Choose one)

- I NEVER had an erection when I wanted one
- I had an erection LESS THAN HALF the time I wanted one
- I had an erection ABOUT HALF the time I wanted one
- I had an erection MORE THAN HALF the time I wanted one
- I had an erection WHENEVER I wanted one

28. Overall, how would you rate your ability to function sexually **during the past 4 weeks?** (Choose one)

- Very poor
- Poor
- Fair
- Good
- Very good

29. Overall, how big a problem was your sexual function, or lack of sexual function, for you **during the past 4 weeks?** (Choose one)

- No problem
- Very small problem
- Small problem
- Moderate problem
- Big problem

30. How often have you been able to ejaculate or "cum" when having sexual activity?

- All the time
- Most of the time
- About half the time
- Less than half the time
- None of the time / could not ejaculate

31. How would you rate the strength or force of your ejaculation?

- As strong as it always was

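### Three of the six sexual-function items carry a different lay gloss at baseline and at follow-up, so within-arm change in the main HRQOL endpoint could include a wording effect

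*Combined protocol and SAP*

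**What the plan says.** Section 8 (Statistical Considerations) states: "The main HRQOL endpoint of interest is EPIC-26 sexual function". The Protocol Summary lists as a primary endpoint: "Change from Baseline in Patient-Reported Urinary, Sexual, and Bowel Function as Measured on EPIC-26 at 8 Months & 12 Months following Treatment". Section 1.1 sets a descriptive objective as well, to measure HRQOL before treatment and at both follow-ups for each management option, AS included. The hypotheses in section 1.2 are comparative.

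The items are in Appendix A under Sexual Issues. In the Baseline Survey, Q15a reads "Your ability to have an erection (hard on", and the same gloss appears in Q16 ("of your erections (hard on") and Q17 ("How would you describe the FREQUENCY of your erections (hard on"). In the First Follow Up Survey, Q25a reads "Your ability to have an erection (getting hard for sex", and Q26 and Q27 have "of your erections (getting hard for sex". The Second Follow Up Survey repeats the follow-up gloss in Q27a, Q28 and Q29. The documents give no reason for the difference.

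For the patient-reported outcomes, section 8 plans a GEE model with baseline score as a covariate, four treatment indicators with AS as reference, and a time-by-treatment interaction. It reports adjusted differences from AS at each time.

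**The concern.** Change from baseline assumes that the same question was asked twice. The baseline gloss only restates the word erection in lay terms. The follow-up gloss adds a purpose, namely sex. A man whose function has not changed might answer the two versions differently, for example if he has no partner or is not currently sexually active. Any such difference would be counted as change in function.

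What is at stake is chiefly the change reported within each arm. That is what the Protocol Summary endpoint and the section 1.1 objective describe, and no comparison group protects it. For the between-treatment contrasts the question is narrower: whether the wording could act differently in different arms.

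**Working it through.** **Step 1: compare the items.** The documents do not list the items of the EPIC-26 sexual domain or its scoring. I take the domain to be the six items that recur in the same order on all three forms.

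| Item | Baseline | First follow-up | Second follow-up | Gloss |
|---|---|---|---|---|
| Erection, ability | Q15a | Q25a | Q27a | differs from baseline |
| Orgasm | Q15b | Q25b | Q27b | same |
| Erection, quality | Q16 | Q26 | Q28 | differs from baseline |
| Erection, frequency | Q17 | Q27 | Q29 | differs from baseline |
| Overall function | Q18 | Q28 | Q30 | none |
| Overall problem | Q19 | Q29 | Q31 | none |

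Three of six items differ. The response options are the same on all forms. The orgasm item ("Your ability to reach orgasm (climax") keeps its gloss throughout. The two follow-up forms agree with each other, so the 8- versus 12-month comparison is not touched. The recall period also differs between baseline and follow-up; that is a separate matter.

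**Step 2: effect on within-arm change (hypothetical).** Assume each item is scored 0-100 and the domain is the mean of six. If the new gloss moves each of the three items by s points on average, in either direction, the domain moves by 3s/6 = s/2.

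- s = 2: 1.0 point
- s = 5: 2.5 points
- s = 10: 5.0 points

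A second illustration takes a man who answers one level lower on all three items. With equal spacing, a 5-level item steps by 100/4 = 25 and the 4-level item by 100/3 = 33.3, so his score falls by (25 + 33.3 + 25)/6 = 13.9 points. If 10%, 20% or 30% of an arm did so, its mean would fall by 1.4, 2.8 or 4.2 points. None of these inputs comes from the documents.

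**Step 3: effect on the planned contrasts.** Write the follow-up score in arm k as Y + w(k), where w(k) is the mean wording shift in that arm. The contrast of arm k with AS is then biased by w(k) − w(AS), which is zero when the shift is common.

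I checked this in a single-time-point, baseline-adjusted linear model on simulated data. The group sizes are those in section 8: 300 + 280 + 288 + 316 + 333 = 1,517. The means, SDs and treatment effects are assumed.

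- *Uniform shift, s = 2, 5 or 10.* The intercept moves by 1.0, 2.5 or 5.0. No contrast moves beyond rounding error.
- *Shift proportional to the score, −10% to +10% on the three items.* The domain is multiplied by 0.95 to 1.05, and so is every contrast. The simulated RP minus AS difference of −27.3 becomes −25.9 to −28.6. The sign does not change.
- *Differential shift.* This was not simulated. With the illustration in step 2, a 10-percentage-point difference between two arms in the share of men affected gives 0.10 × 13.9 = 1.4 points of bias in their contrast.

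**Step 4: could a differential shift be adjusted away?** The model adjusts for risk group, age, race, Charlson score and baseline HRQOL. Marital status is collected (section 6.1; Baseline Survey Q23) but is not a covariate, and neither is current sexual activity. If the gloss acted through these and they differed by arm, the adjustment would not fully remove the effect. The documents contain nothing that shows whether it does.

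**The case against.** The strongest reply is that only a parenthesis has changed. The word erection and every answer option are the same. All items sit under a sexual-function heading. The quality item is answered by fitness for sexual activity, and the frequency item by erections when wanted, so two of the three were already tied to sexual or wanted erections at baseline. Only the ability item has generic options. Lay glosses vary elsewhere too, as in the item on bleeding with urination, which suggests loose editing and not an intended change of construct. The planned analysis is comparative, every arm receives the same forms, and a common shift drops out.

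Most of this stands. It limits how large a wording effect is likely to be, and it protects the treatment contrasts against a shared shift. It does not protect the within-arm change, which the protocol also sets out to measure. Nor does it show that the effect is nil.

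A reader might go further and infer that every arm's reported change contains a spurious reduction, or that the treatment comparisons are biased. The documents support neither. They give no direction for the effect, men already at the lowest answer cannot move lower, and nothing links the reading of the gloss to treatment arm, partner status or sexual activity.

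**Conclusion.** The inconsistency is certain: half of the items in the main HRQOL endpoint are glossed differently before and after treatment. The consequence is only a possibility. Within-arm change from baseline, including the change in AS itself, could contain a wording effect of unknown size and direction.

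The planned differences from AS are unaffected by a shift common to all arms. They would be biased only if the wording acted differently by arm or by level of function, which the documents neither show nor exclude.

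Every point figure above is hypothetical. Each rests on assumed equal-weight 0-100 scoring and on assumed shifts. The documents give no SD, effect size or important difference for this endpoint against which to judge them. The matter is worth correcting because correction is cheap; it does not undermine the comparative analysis.

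**What to change.** **Before follow-up forms are sent:** use one identical gloss for the three erection items on all three surveys, for example the baseline wording. Consistency matters more than which gloss is chosen. This means one parenthesis in six lines: Q25a, Q26 and Q27 of the first follow-up and Q27a, Q28 and Q29 of the second.

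**If follow-up forms have already been returned:** either keep the follow-up wording constant, which preserves the 8- versus 12-month comparison, or change it and record the form version for each response. Rest inference on the adjusted differences from AS that section 8 already plans. State the wording difference as a limitation on within-arm change, naming AS explicitly, because comparison with AS cannot repair AS's own change. Label any quoted size of the effect as hypothetical.

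**Cost:** a minor IRB amendment and no extra questions for participants. A change made mid-study creates a mixed-version period that must be flagged, and some men could receive different wording at 8 and 12 months.

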### **Demographic Questions**

21. What is your ethnicity?

- Hispanic or Latino
- Not Hispanic or Latino

22. What is your race? (Choose all that apply)

- White or Caucasian
- Black or African-American
- Asian
- Native Hawaiian or Other Pacific Islander
- Native American or Alaska Native

23. What is your current marital status?

- Single or never married
- Married or domestic partnership
- Divorced
- Widowed
- Separated

24. What is your current employment status?

- Working full time
- Working part time
- Retired
- Unemployed or looking for work
- On disability

25. What is the HIGHEST level of education you have completed?

- Grade school or less
- Some high school
- High school graduate or GED
- Vocational school
- Some college
- Associates degree
- College graduate (Bachelor's degree)
- Some graduate education
- Graduate degree

26. What is the total income of your household?

- Less than \$10,000
- \$10,001 to \$20,000
- \$20,001 to \$40,000
- \$40,001 to \$70,000
- \$70,001 to \$90,000
- More than \$90,000

27. What kind of health insurance or health care coverage do you currently have? *(Check all that apply)*

- Private insurance (please select type below):
  - Insurance provided through my current or former employer or union (including Kaiser/HMO/PPO)
  - Insurance provided by another family member (e.g., spouse) through their current or former employer or union (including Kaiser/HMO/PPO)
  - Insurance purchased directly from an insurance company (by you or another family member)
  - Insurance purchased from an exchange (sometimes called Obamacare or the Affordable Care Act)
- Public or government insurance (please select type below):
  - Medicaid or other state provided insurance
  - Medicare/government insurance for age 65 years and older
  - Medicare Advantage
  - MediGAP
- VA (including those who have ever used or enrolled for VA health care)
- I do not have any medical insurance

